4.0 STUDY HYPOTHESES

This is retrospective study hypothesize that:

- A. There is no association between level and duration of hypotension with (i) myocardial infarction (MI), (ii) cerebrovascular accident (CVA), (iii) death in primary total hip arthroplasty patients.
- B. With the use of IV tranexamic acid is administered, the use of deliberate neuraxial anesthesia induced hypotension does not result in a further clinically relevant reduction in calculated blood loss after total hip arthroplasty.

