5.0 STUDY DESIGN

5.1 Endpoints

5.1.1 Primary Endpoint

The primary outcomes are the incidences of:

- i. myocardial infarction (MI)
- ii. cerebrovascular accident (CVA)
- iii. death
- iv. calculated perioperative intraoperative blood loss.

All primary outcomes are events during the inpatients stay.

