7.0 PROCEDURES

The independent variables of interest include extent of intraoperative hypotension (MAP <45, 50, 55, 60 mmHg) and duration of hypotension (5 mins interval). Intraoperative blood loss will be calculated based on pre-operative and post-operative laboratory hemoglobin levels.

The outcome variables include MI, CVA, death, intraoperative blood loss, ARF, pneumonia, arrhythmia, DVT, PE, and number of packed red blood cell (pRBC) transfusions.

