8.0 STATISTICAL ANALYSIS

1. Proposed analysis (e.g., student's t-test, ANOVA, chi-square, regression, etc.):
Two-step logistic regression modeling to determine odds ratios
2. Confidence intervals: 95%
3. Total sample size required: 10,000

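### Section 8.0 leaves two-step logistic regression undefined, with no covariate list or sparse-event method for MI, CVA and death; penalised regression on a fixed pre-operative set would be safer

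*Combined protocol and SAP*

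**What the plan says.** Section 8.0 has three lines: the method, "Two-step logistic regression modeling to determine odds ratios"; 95% confidence intervals; and "Total sample size required: 10,000". The synopsis repeats the method and the interval level. Neither place says what the two steps are.

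Section 5.1.1 lists MI, CVA and death as separate items under "The primary outcomes are the incidences of", with no composite, and restricts them in time: "All primary outcomes are events during the inpatients stay". Hypothesis A in Section 4.0 reads "There is no association between level and duration of hypotension with" these three outcomes. Section 7.0 defines the exposure as "extent of intraoperative hypotension (MAP <45, 50, 55, 60 mmHg) and duration of hypotension (5 mins interval".

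Section 7.1 and the synopsis list the variables to be collected. Neither says which enter the model, how they are chosen, or what happens if events are few. No event rate, effect size, power or exposure distribution is given.

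**The concern.** Two usual readings of the method do badly when events are few. If the steps are univariable p-value screening and then a multivariable model, a handful of events gives the screen little power, so real confounders fail it and are left out. If the steps are a crude model and then a model with everything entered, maximum likelihood has more parameters than events and coefficients run off to infinity.

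This is an observational comparison of an exposure that the anaesthesiologist chooses, so the adjusted odds ratio is only as good as its adjustment. Hypothesis A predicts no association, so an incompletely adjusted or very imprecise odds ratio could be read as support for it.

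**Working it through.** **Plan's own figure.** The 10,000 cannot be reproduced, because no event rate, effect size or power is stated. For scale, with 5,000 per group (assumed), two-sided 0.05 and an odds ratio of 2, power is 0.25 at a reference rate of 0.1% and 0.45 at 0.2%.

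**Candidate covariates.** Section 7.1, without the record number: 7 demographic or ASA + 4 baseline status + 14 comorbidities + 5 medications + 1 blood pressure = 31 pre-operative items. The synopsis adds 16: zip code, insurance, HLD, anxiety, depression, bipolar disorder, schizophrenia, IBS, number of allergies, opioids, ACE inhibitors, calcium antagonists, diuretics, and pre-operative hemoglobin, BUN and creatinine. 31 + 16 = 47. Ten intra-operative drugs and fluids come on top.

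**Events per covariate** (events ÷ covariates). The event counts are assumptions; 10 to 30 events is 0.1% to 0.3% of 10,000.

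| Events | ÷ 31 | ÷ 47 |
|---|---|---|
| 10 | 0.32 | 0.21 |
| 20 | 0.65 | 0.43 |
| 30 | 0.97 | 0.64 |
| 100 | 3.23 | 2.13 |

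The familiar yardstick of ten per covariate would need 310 to 470 events per outcome, an incidence of 3.1% to 4.7%.

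**Empty exposure cells.** If an exposure cell holds 5% of patients (assumed) and has average risk, the chance that it contains no event is (1 − 0.05)^events: 0.60 at 10 events, 0.36 at 20 and 0.21 at 30.

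**Simulation, true odds ratio 1.5.** N = 10,000; 30 binary covariates (prevalence 1% to 55%) and 10 continuous; 8 true confounders; a binary exposure near 50%; about 150 cohorts per scenario (50 for Firth). Median exposure odds ratios at 10 / 20 / 30 events:

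| Sicker patients are | Screened at p<0.05 | Confounders kept, of 8 | All 40, maximum likelihood | All 40, Firth |
|---|---|---|---|---|
| less exposed | 1.17 / 1.29 / 1.27 | 1.2 / 1.9 / 2.2 | 1.69 / 1.60 / 1.52 | 1.74 / 1.58 / 1.47 |
| more exposed | 2.02 / 1.80 / 1.69 | 1.5 / 2.2 / 2.8 | 1.82 / 1.64 / 1.50 | 1.46 / 1.58 / 1.50 |

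With no confounding, screening added no clear bias (1.34 and 1.56 at 10 and 20 events, against 1.44 and 1.59 for the full model). With a true odds ratio of 1, screened medians were 0.85 to 0.88 when sicker patients were less exposed and 1.15 to 1.29 when more exposed.

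The medians carry simulation error. At 10 events the full model's 10th to 90th percentile was 0.67 to 4.93, so the log-scale SD is about (ln 4.93 − ln 0.67) ÷ 2.563 = 0.78. The standard error of a median over 150 runs is then about 1.25 × 0.78 ÷ √150 = 0.08, or roughly 8%. Small differences between columns should not be over-read.

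**Divergence in the full model.** At least one coefficient diverged, or the fit failed, in about 100% of runs at 10 to 30 events, 99% at 50 and 69% to 75% at 100. The binary exposure coefficient itself diverged in 2% to 5% at 10 events and 0% to 1% at 20 or more.

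**Simulation, true odds ratio 2.** 40 covariates, 7 confounders and 10 to 30 events. Ranges of medians pool repeat implementations (400 cohorts per scenario in one, 150 in another):

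- Screened: 1.39 to 1.75 if sicker patients are less exposed; 2.25 to 2.76 if more exposed. Where retention was recorded, 1.5 to 2.9 of 7 confounders were kept.
- Firth with a propensity score: 1.86 to 2.03 and 1.70 to 1.93 respectively.
- At 10 events with sicker patients less exposed, the 5th to 95th percentile was 0.47 to 22 for full maximum likelihood and 0.58 to 7.0 for Firth with a propensity score.

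**The case against.** The best defence is that Section 7.1 is a collection list, not a model. A short fixed covariate list is equally compatible with Section 8.0, and ordinary maximum likelihood on the right 7 confounders did about as well as the penalised method: medians 1.81 to 2.08 for a true value of 2. That stands, with two limits. Someone has to name the right list in advance, and the plan does not. And at 10 events, with sicker patients more exposed, the exposure term still diverged in 8% to 9% of runs.

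Three stronger readings are tempting, and the documents do not support them.

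- *The method understates harm.* A reader might infer this because Hypothesis A predicts no association and the technique is deliberate. It requires sicker patients to be less exposed. Section 2.0 says only that many anaesthesiologists routinely work in a low MAP range. With the opposite pattern, screening overstates harm.
- *The model will fail.* The near-100% divergence counts any coefficient, mostly those of rare comorbidities. With one binary exposure and 20 to 30 events, the full model's exposure odds ratio and coverage were acceptable.
- *About 40 covariates enter, or are screened.* Neither is stated.

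Also fair: coverage of the screened intervals falls only modestly (97%, 94% and 91% at 10, 20 and 30 events with a true value of 1.5 and sicker patients less exposed), because the intervals are wide. The damage is chiefly to the point estimate.

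**Conclusion.** The concern holds in a limited form. As written, Section 8.0 permits an analysis that, at 10 to 30 events per outcome, would leave out most true confounders. In the simulations this moved a true odds ratio of 2 to somewhere between 1.39 and 2.76, depending on who is exposed. The direction is not fixed by the documents. The all-in alternative gives divergent nuisance coefficients and an imprecise exposure estimate at about 10 events. Exposure terms can also fail if MAP thresholds and 5-minute durations are cut into sparse cells.

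This rests on assumed event rates, covariate prevalences and confounder strengths, and on a binary exposure; the graded exposure in Section 7.0 was not simulated. The problem eases with more events but persists: at 100 events screening still kept only 4.8 to 5.6 of 8 confounders. No method restores missing precision. Firth with a propensity score still spanned 0.58 to 7.0 at 10 events. Because a standard method does better than a common reading of the plan, this is worth changing and is more than a request to define a term.

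**What to change.** In Section 8.0, for MI, CVA and death, replace two-step logistic regression with Firth-penalised logistic regression on the MAP and duration exposure, and state how that exposure is coded. Specify:

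- a fixed list of pre-operative covariates named before outcomes are analysed, entered directly or through a propensity score suited to a graded exposure (multi-category or continuous; a binary score or ordinary overlap weights would not fit Section 7.0);
- no selection by p-value;
- no intra-operative or post-operative variables that may respond to hypotension, such as vasopressors, fluids or transfusion;
- profile-likelihood 95% confidence intervals.

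An MI/CVA/death composite may be added as a supportive analysis, with its components still reported. It mixes events of different severity and need not lead.

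The cost is SAP wording, standard software for the penalised fit, and a little more analysis work on data already recorded; a graded propensity score, if chosen, adds some. The statistical price is slight shrinkage: Firth with a propensity score gave medians of 1.70 to 1.93 for a true value of 2 when sicker patients were more exposed.

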9.0 ADVERSE EVENT ASSESSMENT

All Adverse Events (AEs) will be reported in the final study report.
